^m The version of the Achenbach CBCL appropriate to each subject's age should be administered with the following exception: For subjects who completed the CBCL/1½-5 at the Baseline assessment of the primary study and turn 6 years of age within 1 year after the Baseline assessment of the primary study, the CBCL/1½-5 should be completed for 1 year after the Baseline assessment of the primary study, and subsequently the CBCL/6-18 should be completed. The Achenbach CBCL will only be administered in countries where a validated translated version is available.

ⁿ The Bayley-III scales should be completed for subjects <18 months of age at study entry if enrolled in English-speaking countries. The same scale should be completed for 1 year after the Baseline assessment of the primary study, even if the subject turns >18 months of age during that period.

^o The BRIEF-P or BRIEF appropriate for each subject's age should be completed, with the following exception: For subjects who completed the BRIEF-P at the Baseline assessment of the primary study and turn 5 years of age within 1 year after the Baseline assessment of the primary study, the BRIEF-P should be completed 1 year after the Baseline assessment of the primary study, and subsequently the BRIEF should be completed. The BRIEF-P and BRIEF will only be administered in countries where a validated translated version is available.

^p The PedsQL form appropriate for each subject's age should be completed, with the following exception: If a subject ages up to the next form of the PedsQL within 1 year after the Baseline assessment of the primary study, the form that was used at the Baseline assessment should be completed for 1 year after the Baseline assessment of the primary study, and subsequently the form consistent with his/her age at the time of assessment should be completed. The PedsQL will only be administered in countries where a validated translated version is available.

^q Only if LCM will be dispensed for taper.

^r Lacosamide for taper will be dispensed only for subjects who achieve a dose of LCM ≥3mg/kg/day (oral solution) or LCM ≥150mg/day (tablet). It is recommended that the dose be tapered gradually in weekly decrements. A slower taper is permitted, if medically necessary. In case of an emergency, a faster taper is permitted after discussion with the Medical Monitor, whenever possible. Taper of LCM may not be required for some subjects who withdraw from the study prematurely, depending on the treatment option selected by the investigator in consultation with the subject and/or legal representative(s).

^s Subjects and/or legal representative(s) will be reminded to complete the diary on a daily basis. For subjects who enter the Safety Follow-Up Period, the subject diary will be returned at the Safety Follow-Up Visit. Subjects who do not enter the Safety Follow-Up Period will return the diary at V13/TermV.

Table 5-3: Schedule of study assessments: Taper Period and Safety Follow-Up Period

Assessments	Taper Period	Safety Follow-Up Period	
	Taper Visit ^a	Safety Follow-Up Visit ^b	Safety Follow-Up Telephone Call ^c
Concomitant medications	X	X	X
Concomitant AEDs	X	X	X
VNS assessment ^d	X	X	
Physical exam (complete)		X	
Physical exam (brief)	X		
Tanner Stage ^e		X	
Blood pressure and pulse rate (including orthostatic assessments in ambulatory subjects)	X	X	
Body weight and height	X	X	
Neurological exam (complete)		X	
Neurological exam (brief)	X		
12-lead ECG ^f	X	X	
Clinical chemistry and hematology blood sample	X	X	
Endocrinology blood sample	X	X	
Urinalysis (subjects aged ≥5 years) ^g	X	X	
Serum pregnancy test ^h	X	X	
C-SSRS ⁱ	X	X	
LCM return/compliance	X		
Subject diary ^j	X	X	
AE reporting	X	X	X ^k
Health care resource use	X	X	

AE=adverse event; AED=antiepileptic drug; C-SSRS=Columbia-Suicide Severity Rating Scale; ECG=electrocardiogram; IXRS=interactive voice/web response system; LCM=lacosamide; Term=Termination; V=Visit; VNS=vagus nerve stimulation

^a The Taper Period (up to 4 weeks, depending on dose level achieved, see Section 7.2.2 for details) will be required for subjects who complete the study or withdraw from treatment during the study if the following doses are achieved: LCM ≥3mg/kg/day for subjects receiving oral solution, or LCM ≥150mg/day for subjects taking tablets. The Taper Visit will be performed at the end of the Taper Period. Taper of LCM may not be required for some subjects who complete the study or withdraw from the study prematurely, depending on the treatment option selected by the investigator in consultation with the subject and/or legal representative(s).

^b Subjects who complete the study or withdraw prematurely from the study, and who discontinue use of LCM, should complete a Safety Follow-Up Visit 2 weeks (±2 days) after the final dose of LCM (including that from LCM taper). The Safety Follow-Up Visit is not required for subjects who complete the study and do not undergo taper of LCM. The Safety Follow-Up Visit is not required for subjects who participate in EP0151 or EP0152.

Table 5-3: Schedule of study assessments: Taper Period and Safety Follow-Up Period

Assessments	Taper Period	Safety Follow-Up Period	
	Taper Visit ^a	Safety Follow-Up Visit ^b	Safety Follow-Up Telephone Call ^c

[figure not shown]
- ^c The Safety Follow-Up Telephone Call occurs 30 days (-1/+3 days) after the final dose of LCM. The Safety Follow-Up Telephone Call is not required for subjects who participate in EP0151 or EP0152.
- ^d Only applicable for subjects with an implanted VNS device.
- ^e The Tanner Stage will be performed only for subjects who are pubescent at V1 or who enter puberty during the course of the study.
- ^f A 12-lead ECG (2 interpretable recordings approximately 20 to 30 minutes apart) will be performed prior to any blood draws and vital signs and, if possible, after the subject has been in a supine position for approximately 5 minutes preceding the ECG recording.
- ^g For subjects aged ≥ 5 years, urine assessments will be based on the subject's ability to void and staff's ability to collect urine (in an appropriate container).
- ^h For female subjects of childbearing potential.
- ⁱ For all subjects ≥ 6 years of age, the "Since Last Visit" version of the C-SSRS should be completed. If a subject becomes 6 years of age during the study, the "Already Enrolled" version of the C-SSRS should be used at the first visit at which the subject is 6 years of age and the "Since Last Visit" version at subsequent visits.
- ^j Subjects and/or legal representative(s) will be reminded to complete the diary on a daily basis. For subjects who enter the Safety Follow-Up Period, the subject diary will be returned at the Safety Follow-Up Visit. Subjects who do not enter the Safety Follow-Up Period will return the diary at V13/Term V.
- ^k If an AE is reported at this telephone contact, the investigator will follow the AE until it has resolved, has a stable sequelae, the investigator determines that it is no longer clinically significant, or the subject is lost to follow up.

[figure not shown]
5.3 Schematic diagram

Figure 5-1 presents schematic diagrams of dosing for EP0034.

PUBLIC COPY
This document cannot be used to support any marketing authorization application and any extensions or variations thereof.

Figure 5-1: Schematic diagram

LCM=lacosamide; SFU=Safety Follow-Up; TC=telephone contact; V=visit

Note: Taper of LCM may not be required for some subjects who complete the study or withdraw from the study prematurely, depending on the treatment option selected by the investigator in consultation with the subject and/or legal representative(s) or for subjects who participate in EP0151 or EP0152.

5.4 Rationale for study design and selection of dose

Epilepsy is a condition for which an improved benefit/risk ratio for medicinal products remains a challenge; this is especially true for pediatric patients.

EP0034 will provide continued availability of LCM to subjects who have completed SP0969, which is a Phase 3, multicenter, double-blind, randomized, placebo-controlled, parallel-group study to evaluate the efficacy and safety of LCM as adjunctive therapy in pediatric subjects with epilepsy ≥ 4 years to < 17 years of age with partial-onset seizures. EP0034 will also be open to subjects who complete SP0967, which is the planned confirmatory study for LCM as adjunctive therapy in pediatric subjects with epilepsy aged ≥ 1 month to < 4 years with partial-onset seizures.

Dose selection in EP0034 is based on the primary studies (ie, SP0969 and SP0967). During EP0034, investigators will be allowed to increase or decrease the dose of LCM to optimize tolerability and seizure reduction for each subject. Lacosamide doses may be increased up to a maximum of LCM 600mg/day or 12mg/kg/day, whichever is lower based on body weight.

6 SELECTION AND WITHDRAWAL OF SUBJECTS

6.1 Inclusion criteria

To be eligible to participate in this study, all of the following criteria must be met:

1. An Institutional Review Board (IRB)/Independent Ethics Committee (IEC) approved written Informed Consent form (ICF) is signed and dated by the subject or legal representative. The ICF or a specific Assent form, where required, will be signed and dated by minors.
2. Subject has completed the Transition Period of SP0967 or SP0969 for the treatment of uncontrolled partial-onset seizures in pediatric epilepsy.
3. Subject is expected to benefit from participation, in the opinion of the investigator.
4. Subject/legal representative is considered reliable and capable of adhering to the protocol (eg, able to understand and complete diaries), visit schedule, and medication intake according to the judgment of the investigator.
5. Subject is male or female aged 1 month to ≤ 17 years.
6. Subject has a diagnosis of epilepsy with partial-onset seizures.

6.2 Exclusion criteria

Subjects are not permitted to enroll in the study if any of the following criteria is met:

1. Subject is receiving any investigational drugs or using any experimental devices in addition to LCM.
2. Subject meets a mandatory withdrawal criterion (ie, MUST withdraw criterion) for SP0967 or SP0969, or is experiencing an ongoing serious AE (SAE).
3. For subjects ≥ 6 years of age, subject has a lifetime history of suicide attempt (including an actual attempt, interrupted attempt, or aborted attempt), or has suicidal ideation in the past 6 months as indicated by a positive response ("Yes") to either Question 4 or Question 5 of the Columbia-Suicide Severity Rating Scale (C-SSRS) at Visit 1.

5. Female subject who is pregnant or nursing, and/or a female subject of childbearing potential who is not surgically sterile or does not practice 1 highly effective method of contraception (according to the International Council for Harmonisation [ICH] guidance defined as those that result in a failure rate <1% per year when used consistently and correctly), unless sexually abstinent, for the duration of the study. Female subject of childbearing potential taking enzyme-inducing antiepileptic drugs (EI-AEDs: carbamazepine, phenytoin, barbiturates, primidone, topiramate, oxcarbazepine) who is not surgically sterile or does not practice 1 highly effective method of contraception according to the World Health Organization recommendation (ie, depot medroxyprogesterone acetate, norethisterone enantate, intrauterine devices, combined injectables, and progestogen implants) with administration of EI-AEDs OR does not practice 2 combined methods of contraception (ie, combined hormonal contraception plus barrier method with spermicidal agent), unless sexually abstinent, for the duration of the study.
6. Subject has >2x the upper limit of normal (ULN) of any of the following: ALT, AST, ALP, or >ULN total bilirubin ($\geq 1.5 \times \text{ULN}$ total bilirubin if known Gilbert's syndrome). If subject has elevations only in total bilirubin that are >ULN and <1.5xULN, fractionate bilirubin to identify possible undiagnosed Gilbert's syndrome (ie, direct bilirubin <35%).

For enrolled subjects with a Baseline result >ULN for ALT, AST, ALP, or total bilirubin, a Baseline diagnosis and/or the cause of any clinically meaningful elevation must be understood and recorded in the electronic Case Report form (eCRF).

6.3 Withdrawal criteria

Subjects are free to withdraw or the subject's legal representatives are free to withdraw the subject from the study at any time, without prejudice to their continued care.

Participation in this study **must** be discontinued for any of the following reasons:

1. Subject experiences intolerable AEs, including clinically relevant abnormal laboratory findings that, in the opinion of the investigator, preclude further participation in the study.
2. The sponsor or a regulatory agency requests withdrawal of the subject.
3. Subject has a QTc interval ≥ 500 ms that is confirmed by a cardiologist over read on any ECG.
4. Subject develops a second-degree atrioventricular (AV) block while awake or develops a third-degree AV block.
5. For subjects ≥ 6 years of age, subject has actual suicidal ideation since last visit as indicated by a positive response ("Yes") to either Question 4 or Question 5 of the C-SSRS. The subject should be referred immediately to a Mental Healthcare Professional and must be withdrawn from the study.
6. Subject is unwilling or unable to continue or legal representative is unwilling or unable to allow the subject to continue in the study.
7. Investigator decides that withdrawal from further participation would be in the subject's best interest.
9. Female subject who achieves menarche during the study and does not practice contraception as provided in Exclusion Criteria 5 unless sexually abstinent.

10. Subject becomes pregnant, as evidenced by a positive pregnancy test.

Participation in this study **may** be discontinued for any of the following reasons:

1. Any clinically relevant change in medical or psychiatric condition (if, in the opinion of the investigator, the condition warrants discontinuation from the study).
2. Subject requires a medication that is not permitted by the protocol (see Section 7.8.1).
3. Subject and/or legal representative is noncompliant with study procedures or medication, in the opinion of the investigator.

Subjects discontinuing LCM for any reason should taper off medication as described in Section 7.2.2. Whenever possible, these cases should be discussed with the Medical Monitor prior to withdrawing the subject from the study.

Investigators should attempt to obtain information on subjects in the case of withdrawal or discontinuation. For subjects considered as lost to follow-up, the investigator should make an effort (at least 1 phone call and 1 written message to the subject and/or legal representative), and document his/her effort (date and summary of the phone call and copy of the written message in the source documents), to complete the final evaluation. All results of these evaluations and observations, together with a narrative description of the reason(s) for removing the subject, must be recorded in the source documents. All subjects who withdraw from the study due to an AE must be followed until resolution of the event or until the event is considered stable. The eCRF must document the primary reason for withdrawal or discontinuation.

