6.3.1 Potential drug-induced liver injury IMP discontinuation criteria

Subjects with potential drug-induced liver injury (PDILI) must be assessed to determine if investigational medicinal product (IMP) must be immediately and permanently discontinued. In addition, all concomitant medications and herbal supplements that are not medically necessary should also be discontinued.

The PDILI criteria below require immediate and permanent discontinuation of IMP:

- Subjects with either of the following:
 - ALT or AST $\geq 5 \times \text{ULN}$
 - ALT or AST $\geq 3 \times \text{ULN}$ and coexisting total bilirubin $\geq 2 \times \text{ULN}$

The PDILI criterion below requires immediate discontinuation of IMP:

- Subjects with ALT or AST $\geq 3 \times \text{ULN}$ who exhibit temporally associated symptoms of hepatitis or hypersensitivity. Hepatitis symptoms include fatigue, nausea, vomiting, right upper quadrant pain or tenderness. Hypersensitivity symptoms include fever (without clear alternative cause), rash, or eosinophilia (ie, $>5\%$).

The PDILI criterion below allows for subjects to continue on IMP at the discretion of the investigator.

- Subjects with ALT or AST $\geq 3 \times \text{ULN}$ (and $\geq 2 \times$ Baseline), and $< 5 \times \text{ULN}$, total bilirubin $< 2 \times \text{ULN}$, and no eosinophilia (ie, $\leq 5\%$), with no fever, rash, or symptoms of hepatitis (eg, fatigue, nausea, vomiting, right upper quadrant pain or tenderness)

Evaluation of PDILI must be initiated as described in Section 10.6.1. If subjects are unable to comply with the applicable monitoring schedule, IMP must be discontinued immediately.

Investigators should attempt to obtain information on subjects in the case of IMP discontinuation to complete the final evaluation. Subjects with PDILI should not be withdrawn from the study until investigation and monitoring are complete. All results of these evaluations and observations, as well as the reason(s) for IMP discontinuation and subject withdrawal (if applicable), must be recorded in the source documents. The eCRF must document the primary reason for IMP discontinuation.

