10.6.1 Liver function tests and evaluation of PDILI

The PDILI IMP discontinuation criteria for this study are provided in Section 10.6.1.2, with the accompanying required follow-up investigation and monitoring detailed below. All PDILI events must be reported as an AE and reported to the study site and sponsor within 24 hours of learning of their occurrence. Any PDILI event that meets the criterion for potential Hy’s Law must be reported as an AE of special interest (see Section 10.3), and, if applicable, also reported as an SAE (see Section 10.2).

Evaluation of PDILI consists of the diagnostic testing and continued monitoring included in Table 10–3 (specific tests dependent on laboratory results and corresponding symptoms) and consultation with a local hepatologist (if applicable; discussed in Section 10.6.1.1). The local

hepatologist is the expert usually consulted by the treating physician for assessment and management of potential hepatic disease. This would usually be a hepatologist, but may be a gastroenterologist. Additional investigation and monitoring may be required and adapted based on the diagnosis after the cause of the liver injury/abnormality is confirmed (details in Section 10.6.1.4).

The results of all monitoring, including laboratory testing and other testing, should be made available to the study site and sponsor.

All initial tests resulting in abnormal hepatic laboratory values need to be repeated, but appropriate medical action must not be delayed waiting for the repeat result.

If tests are done locally for more rapid results, a concurrent sample should also be sent to the central laboratory whenever possible. Medical care decisions are to be made initially using the most rapidly available results and a conservative approach must be taken if the results from the 2 laboratory tests are significantly different. Data from the local and central laboratory are to be recorded on the applicable eCRF pages.

When IMP is discontinued, all concomitant medications and herbal supplements that are not medically necessary should also be discontinued. In these cases, the investigator should also consider dose reduction for medically necessary concomitant medication and consider changing any medically required concomitant medication known to be hepatotoxic to a suitable alternative.

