When IMP is stopped due to PDILI (as described in Section 6.3.1), IMP must be permanently discontinued unless a subsequent alternative diagnosis fully explains the hepatic findings. Rechallenge with a substance potentially causing drug-induced liver injury is dangerous, may be fatal, and must not occur.

Table 10–3 below summarizes the approach to investigate PDILI.

Table 10–3: Required investigations and follow up for PDILI

Laboratory value			Immediate		Follow up	
ALT or AST	Total bilirubin	Symptoms ^a of hepatitis or hypersensitivity	Consultation requirements	Actions	Testing	Evaluation
≥3xULN	≥2xULN ^b	NA	Hepatology consult. ^c	Immediate, permanent IMP discontinuation.	Essential: Must have repeat liver chemistry values and additional testing completed ASAP (see Section 10.6.1.3); recommended to occur at the site with HCP.	Monitoring of liver chemistry values at least twice per week until values normalize, stabilize, or return to within Baseline values. ^d
≥5xULN	NA	Medical Monitor must be notified within 24 hours (eg, by laboratory alert) and subject discussed with Medical Monitor ASAP.				
≥3xULN	NA	Yes		Immediate, permanent IMP discontinuation.		
≥3xULN (and ≥2x Baseline) and <5xULN	<2xULN	No	Discussion with Medical Monitor required if the criterion that allows for IMP continuation is met.	Further investigation – immediate IMP discontinuation not required (see Section 10.6.1.2).	Not required unless otherwise medically indicated (at discretion of investigator).	
≥5xULN (and ≥2x Baseline)	<2xULN	No	Discussion with Medical Monitor required.	Immediate, permanent IMP discontinuation.	Essential: Every attempt must be made to have repeat liver chemistry values and additional testing completed within 48 hours at the site with HCP (see Section 10.6.1.3).	Monitoring of liver chemistry values at least twice per week until values normalize, stabilize, or return to within Baseline values. ^d

Table 10–3: Required investigations and follow up for PDILI

Laboratory value			Immediate		Follow up	
ALT or AST	Total bilirubin	Symptoms ^a of hepatitis or hypersensitivity	Consultation requirements	Actions	Testing	Evaluation

ALP=alkaline phosphatase; ALT=alanine aminotransferase; ASAP=as soon as possible; AST=aspartate aminotransferase; HCP=healthcare practitioner; IMP=investigational medicinal product; NA=not applicable; PDILI=potential drug-induced liver injury; ULN=upper limit of normal

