10.6.1.1 Consultation with Medical Monitor and local hepatologist

Potential drug-induced liver injury events require notification of the Medical Monitor within 24 hours (eg, by laboratory alert), and the subject must be discussed with the Medical Monitor as soon as possible. If required, the subject must also be discussed with the local hepatologist. The local hepatologist is the expert usually consulted by the treating physician for assessment and management of potential hepatic disease. This would usually be a hepatologist, but may be a gastroenterologist. If determined necessary, this discussion should be followed by a full hepatology assessment (see Section 10.6.1.3) and SAE report (if applicable).

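### The instruction to taper lacosamide after any discontinuation has no exception for the immediate stop required in potential drug-induced liver injury

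*Protocol*

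**What the plan says.** **Taper.** Section 6.3 closes its withdrawal lists with "Subjects discontinuing LCM for any reason should taper off medication as described in Section 7.2.2". The Summary says that subjects who withdraw from treatment should taper; Section 5.1 and Table 5-3 footnote a say that the Taper Period is required for them. In these three places the trigger is a dose of at least 3 mg/kg/day (oral solution) or 150 mg/day (tablets). Section 7.2.2 uses the same thresholds, recommends weekly decrements (Tables 7-2 and 7-3), and allows a faster taper in an emergency. It also carries a waiver, depending on the treatment option chosen, for some subjects who complete the study or leave it early. The Summary, Section 5.1 and Table 5-3 footnote a carry that waiver too.

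**Liver stop.** For ALT or AST at or above 5xULN, or at or above 3xULN with total bilirubin at or above 2xULN, Section 6.3.1 says "The PDILI criteria below require immediate and permanent discontinuation of IMP". For ALT or AST at or above 3xULN with symptoms of hepatitis or hypersensitivity it says "The PDILI criterion below requires immediate discontinuation of IMP". Table 10-3 gives the action as "Immediate, permanent IMP discontinuation", and Section 10.6.1 adds that "IMP must be permanently discontinued unless a subsequent alternative diagnosis fully explains the hepatic findings". Section 6.3.1 also says "Subjects with PDILI should not be withdrawn from the study until investigation and monitoring are complete".

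**The concern.** A child whose liver tests meet a stop criterion, and who is on a dose above the threshold, falls under two instructions that cannot both be carried out: stop now, or step down over weeks. The taper text does not mention PDILI or Section 6.3.1, the liver text does not mention the taper, and nothing says which prevails.

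Patient safety is at stake, not an estimate. A site that follows Section 6.3 or the withdrawal-from-treatment wording as written keeps a child with suspected liver injury on LCM against the protocol's own stop rule.

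**Working it through.** There is no planned figure to reproduce. The check sets the passages side by side and then bounds the extra exposure from the taper tables.

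**1. Does the taper text reach PDILI subjects?** Section 6.3 speaks of discontinuing LCM for any reason, which includes a liver stop. The Summary, Section 5.1 and Table 5-3 footnote a are triggered by withdrawal from treatment. A PDILI subject stops LCM first and stays in the study until monitoring ends, so this wording fits. Sections 8.1.13 and 8.2 are triggered by leaving the study and are not the source of the conflict.

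**2. Does the dose threshold remove the conflict?** No. The starting doses in Section 7.2.1 are 10 mg/kg/day, 6 mg/kg/day and 300 mg/day, all above 3 mg/kg/day or 150 mg/day. Only subjects reduced below the threshold escape, for example those at the Table 7-1 minima of 2 mg/kg/day and 100 mg/day.

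**3. Does an existing clause exempt PDILI?**
- The emergency clause in Section 7.2.2 still prescribes a taper, only a quicker one.
- The waiver is worded for subjects who complete or withdraw from the study. It names entrants to EP0151 and EP0152 in Sections 5.1 and 7.2.2, but nowhere PDILI.
- The waiver is also used unevenly. Section 5.1 contrasts waived subjects with those who leave early and discontinue LCM, who should taper. Section 8.1.13 sends waived subjects to a visit timed from the last LCM dose, which suggests that they may have stopped.

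**4. Extra LCM after a liver stop.** If Section 6.3.1 is followed, it is 0. Otherwise, total = 7 x (sum of the weekly daily doses), from Tables 7-2 and 7-3:

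| Dose at stop | First day | Full taper | Full-dose days |
|---|---|---|---|
| 10 mg/kg/day | 8 mg/kg | 7 x (8+6+4+2) = 140 mg/kg, 4 weeks | 140/10 = 14 |
| 6 mg/kg/day | 4 mg/kg | 7 x (4+2+2) = 56 mg/kg, 3 weeks | 56/6 = 9.3 |
| 300 mg/day | 200 mg | 7 x (200+100+100) = 2800 mg, 3 weeks | 2800/300 = 9.3 |

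The first-day column is the total if the 24-hour notification of the Medical Monitor ends the taper; that is an assumption. Across all rows the full-taper totals run from 7 x (2+2) = 28 to 7 x (9+6+4+2) = 147 mg/kg, and from 7 x (100+100) = 1400 to 7 x (500+300+200+100) = 7700 mg.

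**The case against.** The strongest reply is that no careful site would be misled. The liver rule is specific and mandatory, whereas Section 6.3 and the Summary say only that subjects should taper. Section 10.6.1 says "appropriate medical action must not be delayed waiting for the repeat result". Section 10.6.1.1 says "Potential drug-induced liver injury events require notification of the Medical Monitor within 24 hours". Section 11.1 tells investigators to act against an immediate hazard. Pregnancy is a precedent: it is a mandatory withdrawal reason in Section 6.3, yet Section 10.1.6 permits an immediate stop without any exception in the taper text. Section 6.3 can also be read as concerning study withdrawal, since its next sentence is about discussing cases before withdrawing the subject. Finally, the waiver leaves room for judgement.

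Much of this stands. It makes a multi-week taper after a liver stop unlikely. A reader might infer that the protocol imposes the taper by dose alone; it does not, because the Summary, Section 5.1 and Table 5-3 footnote a carry the waiver alongside the threshold, and Section 6.3 reaches it through Section 7.2.2.

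The reply does not remove the conflict. The Section 6.3 sentence is about discontinuing LCM, not leaving the study, and it directly precedes Section 6.3.1. Section 5.1 and Table 5-3 footnote a call the taper required. The waiver is not worded for subjects held in the study. The pregnancy text spells out an immediate stop and down-titration as alternatives; the liver text has nothing equivalent.

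**Conclusion.** The conflict is real and present in the current protocol text. It is limited to PDILI criteria that mandate a stop, at doses at or above the taper threshold. It does not arise under the PDILI criterion that lets LCM continue at the investigator's discretion.

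A reader might infer that children with suspected liver injury would receive weeks of further LCM. The documents do not support that. Section 6.3.1 would probably prevail at most sites, Section 7.2.2 only recommends the weekly steps, and the documents give no expected number of PDILI cases. The totals, such as 140 mg/kg over 4 weeks, are upper bounds for a site that follows the taper text literally and in full. The likely extra exposure is nil, or about one day's taper dose if the Medical Monitor ends the taper on notification.

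The change is still worth making, because a safety stop should not depend on sites inferring which rule takes precedence.

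**What to change.** Add to the Section 6.3 sentence and to Section 7.2.2: *except where Section 6.3.1 requires immediate discontinuation of IMP for PDILI, in which case IMP is stopped immediately and Section 7.2.2 does not apply*. Put a cross-reference to this exception in the Summary, Section 5.1 and Table 5-3 footnote a.

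No new clinical instruction is needed on seizure cover after an abrupt stop; that can be settled in the discussion with the Medical Monitor that Section 10.6.1.1 already requires.

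The cost is a short wording change at the next protocol amendment, with whatever approvals Section 13.5 calls for. Data collection, the analysis sets and the SAP are unaffected.
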